5.2 Inclusion Criteria

- i) aged 18 or over
- ii) lifetime diagnosis of Bipolar Disorder (I,II, "other specified bipolar disorder") or Cyclothymic Disorder, according to DSM-V (American Psychiatric Association, 2013)
- iii) mood instability (at least one complete mood episode in the last 5 years, and reported interference of sub-clinical mood symptoms)
- iv) Sufficient competency in Portuguese to be able to complete study measures without the need for translation.
- v) Having access to means to participate in the online group (i.e. access to a stable internet connection, having a functional camera and microphone on their computer, and zoom)

5.3 Exclusion Criteria

- viii) current high risk of suicide (measured through clinical interview)
- ix) Bipolar disorder secondary to an organic cause;
- x) Diagnosis of substance dependence or continuous illicit substance misuse resulting in uncertain primary diagnosis;
- xi) Undergoing an acute episode of mania, hypomania or major depression (at baseline) or not euthymic (cut off YMRS > 8 and HMDS > 8 used);
- xii) Other high-risk pervasive disorders such as Borderline Personality Disorder, persistent self-injury;
- xiii) The person lacks the capacity to consent to treatment, has low insight
- xiv) Receiving psychological intervention tailor-made for BD (if the person is receiving psychological support, the person assessing them will register the recurrence and type of intervention and assess on a case-by-case basis if this treatment is concurrent)

Neither medication status nor the presence of other co-morbid psychiatric conditions (apart from the previously mentioned exclusion of BPD) will serve as exclusion criteria but will be recorded.

Participants will not be denied access to routine care but will have changes to their support and treatment recorded.

The decision to include patients that are receiving some kind of psychological intervention, which is not adapted for BD was made in conscience, under the assumption that this skills training can be useful for people with BD even if they are undergoing psychological treatment that does not address these skills and can thus be useful to deliver parallelly to it. The usual complete DBT treatment also has DBT skills training plus individual therapy, with the addition of this being DBT based. Nevertheless,

it is common to have patients going to the skills groups and receiving parallel individual psychological support in other therapy, and it is seen as useful. By not changing the current conditions of the patients recruited, we are also respecting the ecological validity of the study.

5.4 Recruitment Sites

To establish the feasibility of the full RCT, we will deliver the Bi-REAL programme online with the collaboration and referral of three hospitals in the centre of Portugal: Centro Hospital e Universitário de Coimbra (CHUC), Centro Hospitalar de Leiria (CHL) and Centro Hospitalar do Oeste (CHL) and with the additional collaboration of a national association that supports people with bipolar diagnosis (ADEB¹).

5.5 Treatment Arms

Bi-REAL was developed in consultation with other researchers and clinicians who delivered DBT to people with mood instability. Furthermore, the research team was composed of clinical psychologists and psychiatrists with expertise in DBT and dealing with BD patients. The programme was thus conceptualised respecting the five key principles of DBT: i) clearly structured treatment; ii) application of behavioural therapy; iii) emphasis on validation of emotional response; iv) dialectical stance, balancing acceptance and change; v) integration of mindfulness practice. The programme was thus organised in a pre-session to contextualise the skills training and its principles, where the bio-social model adjusted to BD was presented, and the assumptions and goals of treatments were explained. The 12 sessions were then conceptualised to follow the same structure as the treatment proposed in the skills training manual (Linehan, 2014); the four skills modules of DBT (i.e. mindfulness, interpersonal effectiveness, emotional regulation and distress tolerance), with more sessions being dedicated to emotion regulation (6/12), considering it necessary to dedicate more training and time to this topic. The sessions seek to include examples that people with BD can relate to and cover skills for observing events, thoughts, emotions and bipolar symptoms and skills to down-regulate high emotions and upregulate low/depressive symptoms. The component of interpersonal difficulties will also be covered in detail to help participants develop their skills in order to decrease possible triggering situations of bipolar mood swings. There is an effort to help participants to learn and generalise behaviours through teaching and practice. Homework provides opportunities to generalise these skills across real-world contexts and continue the use of skills beyond treatment end. Moreover, participants can have up to 3 individual sessions (of 30 minutes maximum) delivered online or by

¹ For more information <https://www.adeb.pt/>

telephone to help them generalise skills (a register will be kept with the number of sessions taken by each participant).

5.6 Study Recruitment Plan

Participants will be recruited via i) psychiatric services and specialist appointments for mood disorder and bipolar disorder; ii) ADEB (newsletter and sessions online to associates to raise interest); iii) online support groups for bipolar disorder vii) self-referral (adds online and distribution of flyers and posters in mental health services).

Researchers will be present at the hospitals and ADEBs facilities to recruit potential participants at advised moments (e.g. when they go for their routine appointment, at events for people with BD). Additionally, patients identified by their psychiatrists as a potential participant will be approached by clinicians at their routine appointments, who will briefly explain what the study consists of, and if

permission to contact is given, they will be approached by the research team via telephone/email (according to their mentioned preference).

People who self-refer will be contacted by the research team to discuss the study and then, if the participant wishes to proceed, they will need to sign a consent form and send it to the research team, after which they will be assessed. For the complete study recruitment and procedure flow chart see Appendix 1.

5.7 Procedure

Participants which reveal interest in the study at the screening process will agree a suitable date and time with the researcher (either face-to-face or online) to do the following assessment. The screening interview will allow an explanation of the study details, addressing any queries, and address the suitability of the participant to the study. Individuals deemed ineligible at this stage will be informed accordingly. All participants will be thanked for their collaboration and will be reassured that what they choose to do will have no impact in the care they receive. Eligible participants will then coordinate a convenient date and time with the researcher for the baseline assessment appointment.

At baseline assessment (which can take place face to face or through videocall) the researcher will discuss the study information sheet and request the patient to read the consent form and sign (after asking any additional questions). If the participant needs more time to consider the study, the researcher will reschedule a second moment to allow for the appropriate time for them to consider their participation. In this baseline assessment the participant will undergo a semi-structured clinical-interview (Clinical Interview for Bipolar Disorder; Azevedo et al., nd), and the interviewer will also fill in two additional scales to monitor depressive and hypo/mania symptoms (Hamilton Depression Scale and Young Mania rating Scale, respectively). At this point, the researcher will also ask the necessary questions to understand if the person meets inclusion / exclusion criteria.

If the participant is eligible for the study, they will then complete the baseline self-report measures (see Appendix 3): measures assessed by the clinician will take place during the assessment (i.e. CIBD, YMRS and HMDS), and the self-report measure will be sent via link to be completed online. Participants in the experimental group will additionally fill in an adapted diary card and submit it once a week (between sessions), where they are asked to rate their emotions intensity and use of skills (see Appendix 4). Additionally, after each session participants will be asked to anonymously fill in the Group Session Rating Scale (GSRS; Duncan et al., 2003) which briefly assessed participants experience of the group regarding relationships in the group, goals and topics, approach/method, and overall cohesion. Following randomisation (more details in that section) participants will be followed up by the research team at 3 and 6 months post baseline. At 3 month follow up (post-randomisation) blinding was not

conducted considering the need to conduct a qualitative interview of the intervention programme. Independent clinicians and researchers conducted these interviews, and the qualitative interview was anonymised so that participants could share their experience freely about the facilitators, programme and group. All the assessment moments are described in Appendix 1 and the assessment measures per moment in Appendix 3.

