5.9 Data collection

5.9.1 Feasibility and acceptability of study and treatment:

- Feasibility will be assessed in terms of numbers of patients identified, approached, consented, randomised and completed over the active period of recruitment and treatment, as well as participant attrition from the trial and from treatment.
- To assess acceptability all participants will complete a questionnaire about their experience in the trial, at the end of the programme, and will be interviewed to express what was more and less useful in the programme, suggestions, and skills retention. The participants will also be asked at 6 month follow up what was retained and continues to be used in their daily life, to assess transferability of what was learned.

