5.10 Measures

The following measures where used, to assess diagnosis, clinical symptoms and self report:

Diagnosis and mood episode/functionality/empowerment (completed at baseline and 3, 6 months post baseline):

- Clinical Interview for Bipolar Disorder (CIBD; Azevedo et al., nd) – Clinical semi-structured interview which allows for the diagnosis of Bipolar and Related disorders. It includes an

assessment of mood symptoms interference and empowerment towards bipolar symptomatology by the interviewee – outcomes considered will include empowerment and interference of mood symptoms

- Young Mania Rating Scale - observer rated, measures current mania symptoms
- Hamilton Depression Scale - observer rated, measures current depressive symptoms

5.10.1 Primary outcomes:

- BIPOLAR DISORDER RECOVERY QUESTIONNAIRE (Jones et al., 2013), a 36 item self-report measure that has been developed to measure personal recovery in people with Bipolar Disorder.
- BRIEF QUALITY OF LIFE IN BIPOLAR DISORDER SCALE(Michalak et al., 2010), a self-report measure of quality of life in bipolar disorder that has been specifically designed for and validated with individuals with the condition.

The additional measures selected for this study include secondary outcomes we believe might change due to the skills developed in the programme, and some hypothesised mechanisms of change, providing data on their performance and preliminary analysis of change. Hypothesised treatment targets include difficulties in regulating emotions, hyper/hypo activation, emotional acceptance, emotional awareness, self-reassurance, self-criticism (hated selfxxx) and shame.

5.10.2 Self-report measures of therapy process (completed at baseline, 3, and 6 months post baseline):

- Depression Anxiety and Stress Scale (DASS-21) (Henry & Crawford, 2005) – we will use the depression and anxiety subscales to assess the psychological distress.

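### The 3-month YMRS and HMDS ratings are left unblinded for the sake of a programme interview that does not require it; scoring them first would reduce, not remove, the risk of rater bias

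*Combined protocol and SAP*

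**What the plan says.** Section 5.7 (Procedure) states: "At 3 month follow up (post-randomisation) blinding was not" done, and gives one reason, that this was "conducted considering the need to conduct a qualitative interview of the intervention programme". It adds: "Independent clinicians and researchers conducted these interviews, and the qualitative interview was anonymised". It does not say that the symptom rater was kept unaware of the arm, that the ratings came before the programme interview, or that a different person held that interview.

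Section 5.10 (Measures) schedules the CIBD, YMRS and HMDS at baseline, 3 months and 6 months, and the Appendix 3 table agrees. It describes two of them as scored by an observer: "Young Mania Rating Scale - observer rated, measures current mania symptoms" and "Hamilton Depression Scale - observer rated, measures current depressive symptoms". For the CIBD, the outcomes used are empowerment and interference of mood symptoms, which Section 5.10 says are assessed by the interviewee. In its account of the baseline visit, Section 5.7 groups all three instruments as clinician-assessed: "measures assessed by the clinician will take place during the assessment (i.e. CIBD, YMRS and HMDS".

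For 6 months the documents do not state whether raters are blinded. Section 5.9.1 adds a programme question there: "The participants will also be asked at 6 month follow up what was retained and continues to be used in their daily life".

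**The concern.** The stated reason does not lead to the stated consequence. Whoever holds an interview about the programme must know that the participant attended it. The person scoring mania and depression need not know this before scoring. As written, nothing stops the rater from learning the arm first and then scoring two scales that depend on judgement.

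At stake are the between-arm estimates for YMRS and HMDS. Section 6.2 reports means and standard deviations for all outcomes by arm at each time point and plans mixed models for the time by group interaction. Randomisation follows the baseline assessment (Section 5.8), so baseline ratings cannot be influenced by the arm. Any rater bias would enter only afterwards, and so would appear in the interaction that the models explore. Section 3 makes preliminary improvement part of the study's purpose. Aim 4 in Section 4 lets secondary measures thought to improve with the training inform the choice of a future primary outcome. Aim 3 is to refine procedures for the definitive trial, which could inherit this one.

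**Working it through.** **Text check.** No figure in the plan measures rater bias, so there is none to reproduce. The passages compare as follows.

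| Question | What the documents give |
|---|---|
| Blinded at 3 months? | No (5.7) |
| Reason? | Programme interview only (5.7) |
| Observer-scored measures then due? | YMRS and HMDS (5.10, Appendix 3) |
| Does the interview reveal the arm? | Yes: usefulness of the programme, suggestions, skills retention (5.9.1) |
| Order of ratings and interview? | Not stated |
| Same person for both? | Not stated |
| Blinded at 6 months? | Not stated, but retained skills are asked about (5.9.1) |
| Primary clinical outcomes? | Self-report (5.10.1), completed through an online link (5.7) |

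The programme interview can unblind the rater only if it, or knowledge gathered for it, precedes the scoring. Scoring and locking first closes that route at 3 months. At 6 months it does not close it for a rater who held the same participant's 3-month interview, because that person already knows the arm.

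**Illustration of size (the bias is assumed).**

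Inputs:
- 30 per arm (Section 6.1).
- 17% attrition (Section 6.1). The plan ties this figure to nine months, later than this trial's last visit, so it is borrowed here.
- Two-sided 5% test. The plan states no alpha.
- No true effect, and a simple comparison of two means at one time point.

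Analysed per arm: 30 × (1 − 0.17) = 24.9, taken as 25.

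Standard error of a standardised difference: √(2/25) = 0.283. The 95% half-width is 1.96 × 0.283 = 0.554 SD.

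For a rater shift b in SD units, the rejection probability is 1 − Φ(1.96 − b/0.283) + Φ(−1.96 − b/0.283).

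| Assumed shift (SD) | b/SE | 25 per arm | 24 per arm | 30 per arm |
|---|---|---|---|---|
| 0 | 0 | 5.0% | 5.0% | 5.0% |
| 0.1 | 0.35 | 6.4% | 6.4% | 6.7% |
| 0.2 | 0.71 | 10.9% | 10.7% | 12.1% |
| 0.3 | 1.06 | 18.6% | 18.0% | 21.3% |

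(The b/SE column is for 25 per arm.) In a pilot the estimate matters more than the test. The shift passes one for one into the between-arm difference: 0.2 SD is 0.2/0.554 = 36% of the confidence half-width.

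**The case against.** The best case on the other side is that little in this trial depends on these two scales. The primary clinical outcomes are self-reported. None of the four criteria in Section 4.1 uses a YMRS or HMDS score. Aim 4 relies mainly on completion rates and perceived relevance. Section 6.2 puts description first and calls the models exploratory. Entrants should be euthymic, with cut-offs of 8 on both scales (Section 5.3), which limits the room for apparent improvement. All of this stands and keeps the point modest. It does not make the missing masking necessary.

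The illustration can also be challenged: it shows what an assumed bias would do, not that a bias exists. That is correct, and no more is claimed for it.

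A reader might go further than the documents allow in four ways.

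- **That the CIBD outcomes are equally exposed.** A clinician conducts the interview, but empowerment and interference are assessed by the interviewee, so rater bias bears on them less directly.
- **That one person rates and interviews in one visit, programme questions first.** This is a fair inference from Sections 5.7 and 5.9.1, but neither states it. The Appendix 1 flow chart was not legible in the copy reviewed and might show the order.
- **That independent raters are already in place, so masking needs no staffing.** Section 5.7 says "Independent clinicians and researchers conducted these interviews", but this may refer only to the qualitative interviews. Independence also differs from being unaware of the arm.
- **That reordering alone gives masked scoring.** Participants are told their arm (Section 5.8). Follow-ups also ask about adverse events and medication changes (Section 8.1), and services received are recorded (Section 5.5). Each can reveal the arm.

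Finally, Section 5.7 is partly in the past tense and Section 2 gives a proposed end date of 31.08.2022. If the visits are over, only the reporting part of the fix remains.

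**Conclusion.** The point holds in a limited form. The 3-month follow-up is unblinded, the only stated reason does not require it for the symptom ratings, and YMRS and HMDS therefore carry an avoidable risk of rater bias. The same risk is likely at 6 months, where the blinding status is not given.

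Its size is unknown. Under the assumptions above, shifts of 0.1 to 0.3 SD take a nominal 5% error rate to between 6.4% and 18.6% for the scale concerned. The consequence is confined to secondary, exploratory estimates. The documents do not support the inference that the recovery and quality-of-life results, or the feasibility criteria, are compromised by unmasked raters.

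**What to change.** **At 3 months.** Complete and lock YMRS and HMDS, and the CIBD with them, before any question on the programme, adverse events or services received. Where existing staff allow, use a rater who has not been told the arm. Ask participants beforehand not to mention it. Record whether the rater knew the arm before scoring. This changes only the order within the visit; the suicide-risk monitoring in Section 7.4 stays as planned.

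**At 6 months.** Use the same order. Where existing staff allow, assign a team member who did not hold that participant's 3-month programme interview. Otherwise report the 6-month ratings as unblinded. State the 6-month blinding status in Section 5.7 either way.

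**In reporting.** Label any YMRS and HMDS ratings already taken unblinded as such, and interpret their between-arm estimates with that caution.

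**Cost.** A reordered visit script and one extra item on the form. A separate rater depends on staffing that the documents do not settle, so it is asked for only where available. Some participants will still disclose their arm, so bias is reduced and not removed; the record of rater awareness shows how often this happened.

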5.8 Randomisation Procedure

Following completion of the baseline assessment, eligible participants will be randomised on a 1:1 ratio (minimisation by age and psychological support status [undergoing psychotherapy versus not receiving psychological support]) to Treatment as Usual (TAU) [control arm] or Treatment as Usual plus Bi-REAL programme (TAU + BI-REAL) [intervention arm]. We will perform a stratified block randomization after participant has attended a baseline assessment and has consented to the trial, a member of the research team will enter a set of data on the randomisation website (www.randomization.com). Participants will receive an email informing them of the arm to which they have been allocated. For participants allocated to the intervention arm, they will be informed at the group starting date and time.

5.9 Data collection

5.9.1 Feasibility and acceptability of study and treatment:

- Feasibility will be assessed in terms of numbers of patients identified, approached, consented, randomised and completed over the active period of recruitment and treatment, as well as participant attrition from the trial and from treatment.
- To assess acceptability all participants will complete a questionnaire about their experience in the trial, at the end of the programme, and will be interviewed to express what was more and less useful in the programme, suggestions, and skills retention. The participants will also be asked at 6 month follow up what was retained and continues to be used in their daily life, to assess transferability of what was learned.

5.10 Measures

The following measures where used, to assess diagnosis, clinical symptoms and self report:

Diagnosis and mood episode/functionality/empowerment (completed at baseline and 3, 6 months post baseline):

- Clinical Interview for Bipolar Disorder (CIBD; Azevedo et al., nd) – Clinical semi-structured interview which allows for the diagnosis of Bipolar and Related disorders. It includes an

assessment of mood symptoms interference and empowerment towards bipolar symptomatology by the interviewee – outcomes considered will include empowerment and interference of mood symptoms

- Young Mania Rating Scale - observer rated, measures current mania symptoms
- Hamilton Depression Scale - observer rated, measures current depressive symptoms

5.10.1 Primary outcomes:

- BIPOLAR DISORDER RECOVERY QUESTIONNAIRE (Jones et al., 2013), a 36 item self-report measure that has been developed to measure personal recovery in people with Bipolar Disorder.
- BRIEF QUALITY OF LIFE IN BIPOLAR DISORDER SCALE(Michalak et al., 2010), a self-report measure of quality of life in bipolar disorder that has been specifically designed for and validated with individuals with the condition.

The additional measures selected for this study include secondary outcomes we believe might change due to the skills developed in the programme, and some hypothesised mechanisms of change, providing data on their performance and preliminary analysis of change. Hypothesised treatment targets include difficulties in regulating emotions, hyper/hypo activation, emotional acceptance, emotional awareness, self-reassurance, self-criticism (hated selfxxx) and shame.

5.10.2 Self-report measures of therapy process (completed at baseline, 3, and 6 months post baseline):

- Depression Anxiety and Stress Scale (DASS-21) (Henry & Crawford, 2005) – we will use the depression and anxiety subscales to assess the psychological distress.
- Multidimensional assessment of thymic states (MATHYS) (Henry et al., 2008) - is a visual analogic scale consisting of 20 items. These items corresponded to five quantitative dimensions: emotional reactivity (EM), thought/cognitive processes (CO), psychomotor function (MO), motivation (VO) and sensory perception (SE). These are them grouped and vary into three continuous: Hypo-reactivity/Hyper-reactivity (EM), Retardation/Acceleration (CO, MO), and Decrease/Increase (VO, SE). The range of scores is from 0-200 and it will vary between the continuous with zero corresponding to one end and 200 to the other, and values around 100 will correspond to stability.
- Distress Tolerance Scale (DTS) (Simons & Gaher, 2005) - is a 15 item self-report measure of emotional distress tolerance. Individuals select on a 1-5 likert scale (Strongly Disagree, Mildly

Disagree, Feel Neutral, Mildly Agree, Strongly Agree) about each of the statements about distress tolerance.

- Difficulties in Emotion Regulation Questionnaire (DERS) (Gratz & Roemer, 2004) - is an instrument measuring emotion regulation problems. The 36 items self-report scale asks respondents how they relate to their emotions in order to produce scores on the following subscales: Nonacceptance of emotional responses: tendency to have a negative secondary or non-accepting reaction to one's own distress; Difficulty engaging in goal-directed behaviour: difficulty in concentrating and/or accomplishing tasks when experiencing negative emotions; Impulse control difficulties: difficulty remaining in control of one's behaviour when experiencing negative emotions; Lack of emotional awareness: reflects a lack of awareness or inattention to emotional responses; Limited access to emotion regulation strategies: reflects the belief that there is little one can do to regulate oneself once upset; and Lack of emotional clarity: reflects the extent to which an individual knows and is clear about his or her emotions. This scale measures an integrative conceptualization of emotion regulation as involving not just the modulation of emotional arousal, but also the awareness, understanding, and acceptance of emotions, and the ability to act in desired ways regardless of emotional state.
- Philadelphia Mindfulness Scale (PHLMS) (Cardaciotto et al., 2008) – this scale has 20 items and measures two dimensions of mindfulness: Acceptance and Awareness (having 10 items per subscale, and providing separate scoring for the dimensions and not as a total). This self report scale asks people to assess how much they have experienced each of the described items over the past week, and participants rate from 0-Never, 1-Rarely, 2-Sometimes, 3- Often, to 4-Very often.
- External and Internal Shame Scale (EISS) (Ferreira et al., 2022) – assesses global shame experience, as well as its external and internal dimensions. This scale consists of eight items, generated to measure the four central domains of general feelings of shame, and present in both external and internal shame: inferiority/inadequacy, sense of exclusion, uselessness/emptiness and criticism/judgment. Each of the dimensions is composed of four items: external (e.g., “I feel that others see me as uninteresting”) and internal dimensions (e.g., “I feel that I am different and inferior to the others”), to which the participants must answer using a 5-point scale (0 = “Never” to 4 = “Always”). Scores vary between 0 and 32 points, with higher values indicating higher levels of shame.
- Ruminative Responses Questionnaire (RRQ-10) (Treynor et al., 2003) – a 10-item scale that measures the individuals' tendency to ruminate when in a sad or depressed mood. This scale comprises two subscales: brooding (5 items) and reflection (5 items). To the statement “what

you generally do, not what you think you should do when feel down, sad or depressed” respondents are asked to rate each item on a 4 point scale (1 = “almost never” to 4 = “almost always”). Thus, scores may range between 10 and 40, with higher scores indicating higher levels of ruminative responses styles.

- Forms of Self-Criticising/Attacking & Self-Reassuring Scale (FSCRS) - (Gilbert et al., 2004) is a 22-item self-report questionnaire in which participants are asked to rate how they typically think and react when things go wrong for them. To a first probe statement: “When things go wrong for me...” participants respond on a 5-point Likert scale (ranging from 0 = not at all like me to 4 = extremely like me). A scale has three factors: Inadequate Self (e.g. ‘I think that I deserve my self-criticism’; ‘I remember and dwell on my failings’); Hated Self (e.g. ‘I stop caring about myself’; ‘I do not like being me’); Reassured Self (e.g. ‘I still like being me’; ‘I can feel lovable and acceptable’).

5.10.3 Measures completed session by session by participants in Bi-REAL + TAU condition.

- Online Version of Diary card submitted before each session (see Appendix 4);
- Group Session Rating Scale (GSRS; Duncan et al., 2003) participants are asked to fill in this assessment scale after each session in an anonymous way to decrease social-desirability bias; this measure uses a four-item visual analogue scale designed to assess key dimensions from 0 to 40: Relationship (0 – *“I did not feel heard, understood, respected, and/or accepted by the leader and/ or the group”* to 40 - *“I felt heard understood, respected, and accepted by the leader and the group”*); Goals and Topics (0 – *“We did not work on or talk about what I wanted to work on and talk about”* to 40 - *“We worked on and talked about what I wanted to work on and talk about.”*); Approach or Method (0 – “The leader and/ or the group's approach is not a good fit for me” to 40 – “The Leader and group's approach is a good fit for me.”); and Overall (0 – “There was something missing in group today - I was not engaged” to 40 – “Overall today's group was right for me - I felt engaged”).

